6.2 Treatment Administration

Arm A: 8.0 Gy x 1 fraction to 8.0 Gy total dose.

Arm B: 8.0 Gy x 2 fractions to 16.0 Gy total dose. The two fractions will be separated by 3-7 days.

Simulation of treatment fields is required prior to the first treatment. There must be imaging of treatment verification approved by a radiation oncologist. All fields must be treated each day. Treatment volume will include the radiographic abnormality with at least a 2 cm margin. Treatment of the entire bone is not required.

6.2.1 Retreatment

Previous studies have shown that pain relief from radiotherapy may take several weeks to become apparent. Therefore, patients should not be re-irradiated to the same treatment site for at least 4 weeks after completion of treatment on this study unless the patient has an increase of 2 points on the worst pain score above the nadir or a 25% increase in daily dosage morphine equivalent of pain medication. Dose and fractionation schemes are left to the discretion of the treating radiation oncologist. Cumulative retreatment occurrence will be recorded at the 6 month follow-up visit.

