1.0 Introduction and Background

Bone metastases are not only the most common cause of cancer-related pain, but palliative radiotherapy is prescribed most frequently to relieve symptoms. External beam radiotherapy (EBRT) is a well-established and efficacious method of palliating painful bone metastases (1). Numerous randomized trials have evaluated the potential benefits of certain dose fractionations of EBRT (1-7), yet controversy remains over the optimal treatment schedule. For example, RTOG 97-14 randomized 898 patients with breast or prostate cancer to receive 8 Gy in 1 fraction or 30 Gy in 10 fractions. There was no significant difference in complete or partial pain relief at 3 months. Patients in the single dose group had a significantly higher retreatment rate at 3 months (18% vs. 9%) but a statistically lower toxicity rate (10% vs 17%) (8). An economic analysis of this trial calculated quality-adjusted life year survival to be 7.3 months vs 9.5 months in the two treatment arms. The authors concluded that single fraction was less expensive and more cost-effective (9). Chow et al conducted a systematic review and meta-analysis of randomized palliative radiotherapy trials comparing single fractions to multiple fractions. Twenty-five randomized trials were identified with no significant differences in pain response rates. The likelihood of re-treatment was 2.6-fold higher (95% CI, 1.92-3.47; $P < 0.00001$) in single fraction EBRT arm patients (10).

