2.0 Objectives

2.1 Primary Objective

- 2.1.1 To determine whether 8 Gy x 2 fractions results in lower cumulative re-treatment rates at 6 months post-treatment completion compared to 8 Gy x 1 fraction in solid tumor patients with bone metastases.

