- 4.4.9 When more than one osseous site is to be included into one treatment field, the treating radiation oncologist may use differing field arrangements at her/his discretion, with the fields arranged to provide relatively uniform treatment of the target sites with a minimum of uninvolved normal tissues.
- 4.4.10 For patients who receiving 8 Gy x 2 to an area near or involving either the spinal cord or cauda equina, the spinal cord and cauda equina needs to be contoured. The dose to the countered cord/cauda equina this this region will be limited to 107% of the prescribed dose. If needed, the PTV coverage can be lowered to 85%. If PTV coverage is between 85% and 80%, a minor deviation should be reported. If PTV coverage is below 80%, a major deviation should be reported.

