5.0 Study Outcomes and Study Measures

5.1 Primary Outcome

- 5.1.1 Cumulative re-treatment rates by treatment arm assessed at 6 months post-treatment completion.

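### The sole primary endpoint is an apparently unmasked decision to re-treat with no stated criterion after 4 weeks, so fewer re-treatments after 8 Gy x 2 could partly reflect less willingness to re-irradiate

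*Combined protocol and SAP*

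**What the plan says.** The primary objective (2.1.1) is "To determine whether 8 Gy x 2 fractions results in lower cumulative re-treatment rates at 6 months", and 5.1.1 names one primary outcome: "Cumulative re-treatment rates by treatment arm assessed at 6 months post-treatment completion". Section 11.1 tests it with a one-sided log-rank test that accounts for competing risks, at patient level. Section 11.3 sets the level at 0.2 with 51 patients per arm.

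On when a patient may be re-treated, 6.2.1 says "patients should not be re-irradiated to the same treatment site for at least 4 weeks after completion of treatment on this study unless" a symptom threshold is met; the exception reads "unless the patient has an increase of 2 points on the worst pain score above the nadir or a 25% increase in daily dosage" in morphine equivalents. The next sentence is "Dose and fractionation schemes are left to the discretion of the treating radiation oncologist". No criterion is given for re-treatment after 4 weeks. Appendix J records whether re-treatment occurred and the date of the first one, nothing more.

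Sections 4.1 and 6.2 randomise patients to one or two fractions (8 or 16 Gy in total). They describe no masking, sham fraction or independent adjudication.

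The plan does collect evidence on symptoms. Pain and daily morphine equivalents by arm at 3 and 6 months are secondary outcomes (5.2.1). Section 7.1 defines response and pain progression from pain and analgesics together. Section 11.2 compares responders with non-responders at 3 months by Fisher's exact test. The 6.1 calendar schedules pain scores and bone-pain medications at 1, 2, 3 and 6 months.

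**The concern.** Re-treatment happens when a patient has symptoms and a clinician decides to act. If the clinician knows the site has already had 16 Gy rather than 8 Gy, the second step may differ between arms even when the first does not. The endpoint then mixes less need with less willingness, and both push in the direction of the one-sided alternative.

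Two places in the protocol make this plausible. Section 4.4.10 adds cord contouring and a dose limit only "For patients who receiving 8 Gy x 2 to an area near or involving either the spinal cord or cauda equina", so delivered dose near the cord is treated as mattering more in that arm. The background (1.0) shows that pain and re-treatment can separate. In the cited 8 Gy x 1 versus 30 Gy in 10 fractions trial, "There was no significant difference in complete or partial pain relief at 3 months", yet re-treatment was 18% against 9%. In the meta-analysis, "Twenty-five randomized trials were identified with no significant differences in pain response rates", yet re-treatment was 2.6-fold more likely after a single fraction.

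At stake is what a positive result means. Section 1.1 asks whether the second fraction reduces re-treatment or improves pain control. A difference in willingness could be reported as better disease control, and a one-sided 0.2 level leaves little margin against a modest bias.

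**Working it through.** **1. Reproduce the plan's power (11.3 and the PASS output in 11.6).** Inputs: re-treatment incidence at 3 months 0.18 (control) and 0.10 (8 Gy x 2); competing risk 0.20 in each arm at 3 months; accrual 18, follow-up 6; loss 0.2; one-sided alpha 0.2. These are the values entered in PASS. The text of 11.3 gives a 36-month accrual and places the competing risk at 6 months, which is a separate discrepancy.

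Cause-specific hazard: h = F_ev × [−ln(1 − F_ev − F_cr)] / [3 × (F_ev + F_cr)].
- Control: 0.18 × 0.4780 / 1.14 = 0.0755; competing hazard 0.0839.
- 8 Gy x 2: 0.10 × 0.3567 / 0.90 = 0.0396. Ratio 0.5251.

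Event probabilities averaged over uniform accrual are 0.4138 and 0.2660, as PASS reports. Expected events: 51 × 0.8 × (0.4138 + 0.2660) = 27.7 (PASS 27.5). Power: Φ(√(27.7/4) × 0.644 − 0.8416) = 0.804 (PASS 0.80195). The stated power is correct for its inputs; the issue is what the endpoint measures.

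**2. Control rates for the illustration.** 18% is the planning rate, stated at 3 months. At 6 months the same hazards give 0.0755/0.1593 × (1 − e^(−6 × 0.1593)) = 0.292, rounded to 29%.

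**3. Effect of reluctance when need is equal.** Assumptions, none of them from the documents: true need is the same in both arms, and a fraction w of indicated re-treatments is forgone in the 16 Gy arm only. Simplifications: 51 per arm, complete follow-up, pooled two-proportion z-test with benefit declared if z > 0.8416, exact binomial enumeration with treatment rate p(1 − w).

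| w | p = 0.18 | p = 0.29 |
|---|---|---|
| 0 | 0.193 | 0.209 |
| 0.10 | 0.265 | 0.317 |
| 0.25 | 0.405 | 0.514 |
| 0.40 | 0.574 | 0.717 |

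The first row departs from 0.20 because counts are discrete. With the plan's 20% loss taken off the sample (51 × 0.8 ≈ 41 per arm), the 29% column becomes about 0.29, 0.46 and 0.66 for w = 0.10, 0.25 and 0.40.

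**4. The same question under the plan's own test.** Let r = 1 − w multiply the re-treatment hazard in the 16 Gy arm. Chance of declaring benefit = Φ(√(E/4) × (−ln r) − 0.8416). Example, r = 0.8, PASS follow-up: E = 31.4, so √7.85 × 0.2231 − 0.8416 = −0.216, giving 0.41. Following each patient to 6 months only: E = 51 × 0.8 × (0.292 + 0.242) = 21.8, giving 0.37.

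| r | PASS follow-up | 6 months only |
|---|---|---|
| 1.0 | 0.20 | 0.20 |
| 0.9 | 0.29 | 0.28 |
| 0.8 | 0.41 | 0.37 |
| 0.7 | 0.55 | 0.49 |
| 0.6 | 0.70 | 0.61 |
| 0.525 | 0.80 | 0.71 |

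A simulated log-rank test for the 6-month case gave 0.19, 0.28, 0.39, 0.51, 0.64 and 0.73. The two approaches agree in pattern.

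**5. What the existing symptom analyses can show.** The response test in 11.2 is at 3 months, while the primary runs to 6. Section 11.2 has no rule for pain scores recorded after re-irradiation, so those scores can be altered by the decision in question. No analysis combines progression with re-treatment, and none is linked to reading the primary result.

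**The case against.** The strongest reply has four parts.

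- **The objective is re-treatment itself, not need.** Section 1.1 lists re-treatment and pain control as alternatives. This stands: re-treatment is a legitimate primary endpoint for a phase 2 trial, and one-sided 0.2 is a declared choice. It does not remove the question of how a positive result should be described.

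- **The mechanism is inferred.** A reader might infer from 4.4.10 and the background that clinicians will hold back after 16 Gy. The documents do not support that. Section 4.4.10 is a planning rule for the study course, says nothing about re-treatment, and is irrelevant to sites away from the cord. The background compares a single fraction with 10 or with multiple fractions. A non-significant difference in pain is not equality, and more durable relief would give the same pattern. The discretion sentence in 6.2.1 covers dose and fractionation, and the 4-week rule applies equally to both arms.

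- **Evidence on need already exists.** A reader might infer that the plan has none. In fact 5.2.1, 7.1 and 11.2 would show a warning pattern: fewer re-treatments with no better pain or opioid use. This stands, within the limits in step 5 of the working.

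- **The forgone rates are invented.** True. At 10% forgone and an 18% control rate the rise is only from 0.19 to 0.27, and allowing for losses reduces the figures at 29%.

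**Conclusion.** The point holds as a limit on interpretation. The sole primary endpoint depends on a clinical decision with no described masking and no stated criterion after 4 weeks, so a lower rate after 8 Gy x 2 could partly reflect reduced willingness. That the trial is unmasked is itself inferred from the absence of any masking and from the visible difference between arms. Whether reluctance occurs, and how large it is, cannot be learned from the documents.

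The calculations show only sensitivity. With equal need, forgoing 10% to 40% of indicated re-treatments in one arm moves the chance of declaring benefit from about 0.20 to between 0.27 and 0.57 (18% control rate) or between 0.32 and 0.72 (29%). It would be too strong to say that the primary result will be uninterpretable or that reluctance could never be told apart from benefit: the secondary outcomes give partial evidence. What is missing is an analysis over the full 6 months that handles re-treatment and symptoms together and is tied to the reading of the primary result.

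**What to change.** Keep the primary endpoint, sample size and every clinical rule. In 11.1, pre-specify one supportive analysis with the same competing-risk method: time to the first of re-treatment or pain progression as defined in 7.1, using the pain scores and bone-pain medications already scheduled at 1, 2, 3 and 6 months. Report it beside the primary result. If re-treatment is lower but this estimate does not favour 8 Gy x 2, describe the finding as fewer re-treatments, not as reduced need.

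Use the 7.1 definition rather than the 6.2.1 exception, which gives no reference point for its 25% rise. The SAP should also say how to count a patient whose pain and analgesic dose both rise by the 7.1 amounts: the first progression limb requires stable analgesics and the second allows pain at most 1 point above baseline.

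Adding a reason for re-treatment to Appendix J would not solve this, because it is completed only for patients who were re-treated and cannot reveal re-treatment withheld.

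Cost: a few sentences of SAP text and one analysis, with no new visits. Limits: progression is known only at visits, is affected by missed scores, is self-reported by patients who know their arm, and misses persistent stable pain in non-responders.

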6.3 Duration of Therapy

This is a study of 1 vs. 2 fractions of radiation therapy. For the patients randomized to receive 2 fractions, the treatment may continue unless one of the following criteria applies:

- Unacceptable adverse event(s),
- Patient decides to withdraw from the study, or
- General or specific changes in the patient's condition render the patient unacceptable for further treatment in the judgment of the investigator.

6.4 Duration of Follow Up

Given the variety of non-protocol related treatment, toxicity will be assessed at 30 days after protocol treatment as it is anticipated that this would be part of standard of care for such treatment, and per DSMC requirement. For patients not receiving any additional treatment, additional follow-up visits will occur at 3 and 6 months with follow-up radiologic assessment at the discretion of the treating physician if pain score is >4 as such is standard of care for patients who receive the treatment.

For patients who are undergoing additional therapy of any kind and are being followed by another treating physician, follow-up can be deferred to that treating physician. Toxicity and pain can be assessed via chart review and over the phone for these patients at the appropriate study time points. Patients will be followed in this same manner if being treated at an outside facility. Patients who experience adverse events will be followed every 3-6 weeks until stabilization of the adverse event or until 6 months post-treatment, whichever occurs first.

A patient may remain in the study until one of the following criteria applies:

- Patient decides to withdraw from the study, or

- The patient has completed a minimum of 6 months follow-up.
- Patient enters End of Life Hospice Care and will no longer be followed routinely.

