11.0 Statistical Considerations

11.1 Analysis of Primary Objective

This is a randomized Phase 2 study, with the primary objective to compare the 6-month cumulative incidence of re-treatment rates between groups. Based on previous research, the 8 Gy x 1 fraction [8/1] group (control group) had a retreatment rate of 18% (RTOG Study 97-14). The primary analysis will use a one-sided log-rank test statistic to test the null hypothesis that the re-treatment rates are equal in each group versus that alternative that the re-treatment rates are lower in the 8 Gy x 2 fractions [8/2] group. This analysis will account for competing risks such as death. Analyses will be performed on the patient level, thus if a patient has multiple metastases and any one of these requires retreatment then the patient will be considered retreated.

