11.3 Power and Sample Size

Power calculations were performed using PASS 13. When accounting for competing risks, a one-sided logrank test with an overall sample size of 102 subjects (51 in the control group and 51 in the treatment group) achieves 80% power at a 0.2 significance level to detect a hazard ratio of 0.5251. The study is expected to last for 42 months with an accrual (entry) time of 36 months and a follow-up time of 6 months after the last patient is accrued. The cumulative incidence proportions at time 3 months for the event of interest are 0.18 in the control group (8/1) and 0.10 in the treatment group (8/2). The cumulative incidence proportions at time 6 months for the competing risk factors are 0.20 in the control group and 0.20 in the treatment group. The proportion of subjects lost to follow-up during the entire study is conservatively estimated at 0.2.

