Appendix J – Re-Treatment Data Form

1) Did re-treatment occur? Yes No

a. If yes, when was the first re-treatment? ___/___/___

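### Follow-up stops at hospice entry, and the plan gives no way to learn of later re-treatment or death and no rule for these exits in the competing-risks analysis; censoring them would overstate 6-month incidence.

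*Combined protocol and SAP*

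**What the plan says.** - **Exit rule.** Section 6.4 (Duration of Follow Up) lists three ways in which a patient's participation ends. One is: "Patient enters End of Life Hospice Care and will no longer be followed routinely".
- **Remote follow-up.** The same section allows chart review and telephone contact, for toxicity and pain, in patients who are on other therapy under another physician or treated at an outside facility. Hospice patients are not mentioned there.
- **Endpoint.** Section 5.1 defines it as: "Cumulative re-treatment rates by treatment arm assessed at 6 months post-treatment completion".
- **Capture of re-treatment.** Section 6.2.1 says: "Cumulative retreatment occurrence will be recorded at the 6 month follow-up visit". Appendix J asks whether re-treatment occurred and "If yes, when was the first re-treatment". It has no field for hospice entry, death or last contact.
- **Analysis.** Section 11.1 says: "The primary analysis will use a one-sided log-rank test statistic to test the null hypothesis". It adds: "This analysis will account for competing risks such as death". Hospice is neither named nor excluded, and no censoring rule is given.
- **Losses.** Section 11.3 says: "The proportion of subjects lost to follow-up during the entire study is conservatively estimated at 0.2". It does not say whether hospice exits belong to this 20% or to the 20% competing risk.

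**The concern.** Eligibility requires an expected survival of only 12 weeks (3.1.9), while the endpoint is at 6 months, and the sample-size run assumes 20% competing risk by month 3. Many patients will therefore die during follow-up, and some will enter hospice first. A patient who has left for hospice would not normally attend the 6-month visit at which re-treatment is recorded. Following the plan as written can therefore lose outcome data from the patients nearest death.

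If such a patient is censored at hospice entry, the estimator assumes that the chance of later re-treatment is the same as in patients still followed. That is doubtful for someone in end-of-life care. The competing-risks correction would then work only for deaths that occur without a prior hospice exit, and the estimate would drift towards the uncorrected Kaplan-Meier value. At stake are the absolute 6-month incidence in each arm and the absolute benefit. Two analysts could follow this plan and report different figures.

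**Working it through.** **Inputs.** The software run printed after 11.6 uses re-treatment incidence at 3 months of 0.18 (8/1) and 0.10 (8/2), competing-risk incidence at 3 months of 0.20 in each arm, accrual 18 months, follow-up 6 months, loss 0.2, N = 102 and one-sided alpha 0.2. The text of 11.3 dates the same 0.20 competing risk at 6 months, so both timings are worked below. The share f of competing deaths that first leave through hospice is not in the documents. It is an assumption, shown from 0 to 100%.

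**Step 1: reproduce the plan's figure.** With constant hazards, h = −ln(1 − Fev − Fcr)/3, split in proportion to Fev and Fcr.

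- 8/1: h = −ln(0.62)/3 = 0.1593, so hev = 0.0755 and hcr = 0.0839.
- 8/2: h = −ln(0.70)/3 = 0.1189, so hev = 0.0396 and hcr = 0.0793.
- Hazard ratio = 0.5251.
- Pr(event) = (hev/h) × [1 − (e^(−6h) − e^(−24h))/(18h)] = 0.4138 and 0.2660, mean 0.3399.
- Events = 102 × 0.8 × 0.3399 = 27.7 (27.5 printed).
- Power = Φ(√(E/4) × |ln HR| − 0.8416) = 0.8016 at 27.5 events and 0.8037 at 27.7.

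The printed power is 0.80195, and 11.3 states that the design "achieves 80% power at a 0.2 significance level to detect a hazard ratio of 0.5251". The hazards, hazard ratio and event probabilities match the printout.

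**Step 2: 6-month incidence with every such exit counted as competing.** F(6) = (hev/h) × (1 − e^(−6h)).

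- 8/1: (0.18/0.38) × (1 − 0.62²) = 0.2916.
- 8/2: (0.10/0.30) × (1 − 0.70²) = 0.1700.

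**Step 3: censor a share f at hospice entry.** Replace hcr by hcr × (1 − f) in the same formula. This assumes no re-treatment after hospice entry, hospice entry at the modelled time of the competing event, and the same f in both arms. With the software inputs:

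| f | 8/1 | 8/2 | Difference (points) | Ratio | Excess 8/1 | Excess 8/2 |
|---|---|---|---|---|---|---|
| 0 | 29.2% | 17.0% | 12.2 | 0.583 | – | – |
| 0.25 | 30.8% | 17.9% | 12.8 | 0.583 | 1.6 | 0.9 |
| 0.50 | 32.5% | 18.9% | 13.6 | 0.582 | 3.3 | 1.9 |
| 0.75 | 34.4% | 20.0% | 14.4 | 0.582 | 5.2 | 3.0 |
| 1 | 36.4% | 21.2% | 15.3 | 0.581 | 7.3 | 4.2 |

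**Step 4: repeat with the timing in 11.3.** Solving for 0.18 and 0.10 re-treatment at 3 months with 0.20 competing risk at 6 months gives hev/hcr of 0.0712/0.0465 (8/1) and 0.0375/0.0419 (8/2).

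| f | 8/1 | 8/2 | Difference (points) | Ratio | Excess 8/1 | Excess 8/2 |
|---|---|---|---|---|---|---|
| 0 | 30.7% | 17.9% | 12.8 | 0.583 | – | – |
| 0.25 | 31.6% | 18.4% | 13.2 | 0.582 | 1.0 | 0.5 |
| 0.50 | 32.6% | 19.0% | 13.7 | 0.581 | 2.0 | 1.1 |
| 0.75 | 33.7% | 19.5% | 14.1 | 0.580 | 3.0 | 1.7 |
| 1 | 34.8% | 20.1% | 14.6 | 0.579 | 4.1 | 2.3 |

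**Step 5: effect on the test.** A cause-specific log-rank test removes the patient from the risk set at hospice entry under either label, so its result is identical. For a Gray-type test, simulation (20,000 trials per setting, software hazards, 51 per arm, 6 months of follow-up, no dropout) gave power of about 0.74 with hospice counted as competing and 0.74-0.76 with hospice censored. Type I error, simulated at f = 0.5, was about 0.20 either way.

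**The case against.** A reader might infer that the plan censors hospice patients and refuses to count hospice as a competing event. The documents do not say so. The wording of 11.1 gives death as an example, which leaves room for hospice, and no section prescribes censoring. Section 6.4 stops routine follow-up and does not forbid looking at the chart. This part of the objection stands: the defect is a missing rule and a missing route to the data, and the overestimate is conditional.

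The direction is also not fixed. If a hospice patient is simply entered as not re-treated in a crude proportion, such as the interim two-proportion test in 11.6, nothing is censored and the inflation does not arise. If re-treatment did occur in hospice and was missed, incidence would be underestimated.

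Nor do the documents support a claim that the primary comparison is compromised. The test and the ratio barely move when hospice entry is similar between arms. The shift is also small beside sampling error: with 51 per arm, the simple binomial standard error of the difference is √(0.2916 × 0.7084/51 + 0.17 × 0.83/51) ≈ 0.083, about 8 points.

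Finally, coding every hospice entry as a competing event would change the target to re-treatment before hospice or death. That is a fair objection to using such coding as the main remedy.

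What the objection does not remove is the loss of data. The chart and telephone route in 6.4 is given for other groups and for other outcomes. The duty to report deaths to the DSMC (8.3, Appendix D) reaches only 30 days beyond the last treatment.

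**Conclusion.** The point holds in conditional form. The plan ends follow-up at hospice entry, supplies no means of learning the later outcome, and does not say how these exits enter an analysis whose stated objective is 6-month cumulative incidence.

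If they are censored and later re-treatment is rare, incidence is overestimated. For hospice shares of 25-100%, the excess is 1.6-7.3 points (8/1) and 0.9-4.2 points (8/2) with the software inputs, or 1.0-4.1 and 0.5-2.3 points with the 11.3 timing. The absolute difference is inflated by at most about 3 points and 2 points respectively. The upper ends require every competing death to pass first through unobserved hospice.

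These sizes rest on constant hazards, an assumed hospice share that is equal between arms, and no re-treatment after hospice entry. The consequence is for the absolute estimates. The incidence ratio stays near 0.58 and the one-sided test is essentially unaffected.

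**What to change.** **Section 6.4.** Extend the existing chart-review route to patients who leave for hospice. Record the dates of hospice entry, any re-treatment and death up to 6 months after treatment completion. Appendix J needs fields for hospice entry and death.

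**Section 11.1.** Use those dates in the competing-risks analysis, so that a patient in hospice stays under observation for re-treatment and death. Count hospice entry as a competing event together with death only when later status cannot be found. Report censoring at hospice entry as a sensitivity analysis.

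**Cost.** A few sentences, a small form change and a little chart-review work for the patients concerned. Treatment and sample size are untouched. The remaining weakness is that a rare re-treatment during hospice could be missed if the chart is silent.
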